## ANALYSIS

Peri-prosthetic tissues associated with the Prestige LP™ Cervical Disc will undergo histological evaluation. The histological evaluation will be conducted according to an explant protocol developed by [name]., Professor of Orthopaedic Surgery and Director of Biomaterials Research at the Medical College of Wisconsin. [name] will thoroughly photograph the devices and explanted tissues, perform high resolution radiography on explanted tissue samples, and produce histology slides of the periprosthetic tissues with a histological evaluation of the host response to the device and particulate debris (if present) according to ASTM F981-04.

Following photographic documentation of periprosthetic tissues and all device components, all device components will be dried, left intact, individually packaged, and sent to Exponent at the following address for non-histological implant analysis:

[REDACTED]

## APPENDIX IV

### PRESTIGE LP CERVICAL DISC INFORMATION FOR USE

PCS	Physical Component Summary
SADE	Serious Adverse Device Effect
SF-36	Medical Outcome Study 36-Item Short Form Health Survey

3. Introduction

The PRESTIGE LP™ Cervical Disc is a two-piece articulating device that is inserted into the intervertebral disc space as a single unit at a single or two contiguous cervical levels using an anterior approach. The device is manufactured from a titanium ceramic composite (titanium alloy (Ti-6Al-4V) with 10% Titanium

Carbide) and consists of two low-profile metal plates that interface through a ball and trough mechanism, permitting segmental spinal motion. The superior component of the implant contains the ball portion of the mechanism, and the inferior component contains the trough portion. These two features engage to create an interface designed to allow for motion after implantation. Each component is affixed to the adjacent vertebral body by two rail geometries incorporating anti-migration teeth, which are press fit into two pre-drilled holes in the vertebral bone. The portion of the flat surface between the rails and contacting the vertebral endplate contains commercially pure titanium (CP Ti) plasma thermal sprayed coating designed to permit bony on-growth for additional device incorporation. The remaining portion of the flat surface is titanium ceramic roughened to enhance fixation.

The device is indicated in skeletally mature patients with radiculopathy or myelopathy or both caused by degenerate disc disease from C3-C7. FDA approved PRESTIGE LP™ Supplement P090029/S003 indicating to use at two contiguous levels and to add a 5mm device height for use at either one or two contiguous cervical levels on July 7, 2016. As a condition of approval, the FDA requested the sponsor to investigate the metal concentrations in patients implanted with the PRESTIGE LP™ Cervical Disc at two contiguous levels in the cervical spine in a post approval study.

4. Study Objectives

4.1 Primary Objective

The primary objective of this clinical study is to assess the metal concentrations in the blood serum of patients implanted with the PRESTIGE LP™ Cervical Disc at two contiguous cervical levels for the presence of metal concentrations. The metal to be assessed will include:

- Titanium (Ti)
- Vanadium (V)
- Aluminum (Al)

4.2 Secondary Objectives

Secondary objectives of this study are:

- To evaluate overall success rate.
- To assess the postoperative Neck Disability Index (NDI) score improvement from preoperative;
- To evaluate postoperative Neurological Status change from preoperative.
- To assess the safety of the PRESTIGE LP™ Cervical Disc as reported through AEs and secondary surgeries.
- To assess the postoperative Neck and Arm Pain score change from preoperative.
- To assess the postoperative SF-36 PCS score change from preoperative.

5. Investigation Plan

This will be a prospective study in which up to five investigational sites in the U. S. will be participated. There will be no control group involved. All subjects participated in this study will be required to sign off the informed consent and to meet all of the inclusion and exclusion criteria.

Serum samples will be collected at preoperative, 6 weeks, and 12 months after surgery. Titanium and vanadium concentrations in serum will be analyzed by the Trace Metal Analysis Laboratory (TMAL), Department of Orthopedic Surgery at Rush University Medical Center, following a serum testing protocol developed by the lab. Aluminum in serum will be determined by the Metals Laboratory of Mayo Medical Laboratories Rochester MN.

Demographics and medical and surgical history of the subjects will be collected at preoperative. NDI, neurological, neck and arm pain, pain medication use, and SF-36 PCS Health Survey will be evaluated at preoperative, 6 weeks, 3 months, 6 months, and 12 months after index surgery.

6. Determination of Sample Size

Thirty subjects enrolled at up to five sites will receive the treatments at two contiguous levels using PRESTIGE LP™ investigational devices. This is a single arm study to meet the FDA conditional approval requirements.

7. Statistical Methods

7.1 Study Subjects

7.1.1 Disposition of Subjects

The disposition of subjects including those enrolled, died, withdrawn, and evaluated will be summarized in an accountability table at all follow-up periods.

7.1.2 Protocol Deviations

A study protocol deviation is an instance when the Investigator or site personnel did not conduct the study according to the protocol, clinical investigational plan (CIP), or Investigator agreement. A protocol deviation is classified as a minor or major deviation according to the type of deviations.

7.1.3 Analysis Datasets

7.1.3.1 Primary Analysis Dataset

Primary Analysis will be conducted for the subjects who received the treatment of the PRESTIGE LP™ investigational devices at two contiguous levels. The subjects who enrolled but did not receive any

treatments or who enrolled and received the investigational treatment but exited the study following the surgery with no postoperative follow-up will not be included in this primary analysis. The missing data will not be imputed, and the analysis will be based on the observed data. However, the data prior to the secondary failure will be carried forward to the latest visit for those who had a secondary surgery failure.

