# Prestige LP™2 Metal Concentration Clinical Investigation Plan

MDT16060SD1701

Version 6.0, 08-JUL-2019

Page 25 of 46

Medtronic

Adverse Event (if applicable)		X	X	X	X	X	
Protocol Deviation (if applicable)	X	X	X	X	X	X	
Device Deficiency (if applicable)		X	X	X	X	X	
DEXA Scan*	X						

\*A DEXA Scan was only required if the patient had a risk factor that may be associated with a diagnosis of osteoporosis.

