#### **9.15.3 Adverse Events**

All reported AE information, as defined in Section 11, for a patient after surgery and throughout their participation in the study will be included in the study database and will be analyzed. This analyzed data will be reported to the FDA on an annual basis until the end of the study. AEs related to Medtronic products will be entered into the quality system, at which time further determinations on reporting requirements will be made.

The follow-up report should give full details of the experience, including an assessment of the relationship to the test article(s), and will be sent to the Sponsor promptly. SAEs will then be reported to regulatory authorities by the Sponsor.

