7.1.3.2 Per-Protocol Analysis Dataset

Per-protocol analysis dataset is the subset of the primary analysis dataset. Per-protocol analysis will be performed for the subjects who received the treatment of the PRESTIGE LP™ investigational devices at two contiguous levels but had no major protocol deviations, such as violation of inclusion and exclusion criteria or receiving different treatments other than intended treatment. Per-protocol analysis will only be carried out for overall success status.

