7.2.2 Clinical Data and Analysis

For continuous clinical outcome scores such as NDI, neck pain, arm pain, SF-36 PCS, and surgery data, the summary statistics (n, mean, median, standard deviation, minimum and maximum) at each time point will be presented. The changes from preoperative at each postoperative visit will be analyzed using paired t-test for normally distributed data or Wilcoxon signed-rank test for not normally distributed data.

For categorical clinical outcomes such as overall success, neurological status, NDI success, and pain medication use, frequency and percentage of subjects will be summarized at each time point.

For secondary surgery and adverse events, the rates will be summarized using the life-table method of time-to-event analysis. The Kaplan-Meier analysis will be applied to return-to-work summary.

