7.8 Evaluation of Objectives

7.8.1 Primary Objective and Primary Measurement Analyses

The primary objective of this study is to assess the concentrations of Titanium (Ti), Vanadium (V), and Aluminum (Al) in the blood serum of patients implanted with the PRESTIGE LP™ Cervical Disc at two contiguous cervical levels. The primary measurement analyses associated with the primary objective include:

- The metal concentrations of Titanium (Ti), Vanadium (V), and Aluminum (Al) at preoperative, 6 weeks, and 12 months after index surgery. The summary statistics including n, mean, median, standard deviation, minimum and maximum will be summarized.
- The summary statistics for the changes in the metal concentrations from preoperative will be presented, and the two-sided paired t-test for normally distributed data or Wilcoxon signed-rank test for not normally distributed data will be performed.
- The summary for titanium concentrations from this study will be presented side by side with the one from the Prestige LP™ one-level metal study.
- Pearson correlation analysis will be carried out between the metal concentrations and continuous clinical outcome variables including NDI, arm pain, neck pain, and SF-36 PCS scores at postoperative time points.
- Subgroup analysis of the metal concentrations by binary outcomes including overall success, NDI success and neurological success will be carried out. No statistical inference will be made.

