7.8.2.7 Secondary Surgical Interventions

A time-to-event analysis (life-table method) will be carried out to summarize the secondary surgeries including revision, removal, supplemental fixation, reoperation, and other categories.

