7.8.2.8 Adverse Events

Causality of AEs is categorized as implant associated, surgical procedure associated, implant/surgical procedure associated, undetermined, or not related. AE severity is characterized into four categories: mild (Grade 1), moderate (Grade 2), severe (Grade 3), and life-threatening (Grade 4). For a conservative consideration, implant or implant/surgical procedure associated AEs are considered to be implant associated. Analysis using life-table method will be carried out for all adverse events, implant or implant/surgical procedure associated AEs, Grade 3 or Grade 4 AEs, and Grade 3 or Grade 4 AEs that are implant or implant/surgical procedure associated. In addition, serious adverse device effect (SADE) will be summarized if available.

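### The SAP defines no safety set, and the only set that could serve the adverse-event life tables drops implanted subjects who leave before any follow-up

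*SAP*

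**What the plan says.** SAP 7.1.3 contains two analysis sets.

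- **Primary set (7.1.3.1).** Subjects implanted at two contiguous levels, less those never treated and less those who "received the investigational treatment but exited the study following the surgery with no postoperative follow-up will not be included in this primary analysis".
- **Per-protocol set (7.1.3.2).** A subset of the primary set without major deviations. Its use is limited: "Per-protocol analysis will only be carried out for overall success status".

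The safety sections give a method and no population. SAP 7.2.2: "For secondary surgery and adverse events, the rates will be summarized using the life-table method of time-to-event analysis". SAP 7.8.2.7: "A time-to-event analysis (life-table method) will be carried out to summarize the secondary surgeries". SAP 7.8.2.8: "Analysis using life-table method will be carried out for all adverse events", followed by implant-associated, Grade 3 or 4, and combined subsets.

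Protocol 9.15.3 says that all reported AE information "for a patient after surgery and throughout their participation in the study will be included in the study database and will be analyzed". AE collection begins at the Surgery/Discharge visit (Protocol 9.1, Table 2, and 9.3). The first follow-up visit is at 6 weeks ± 2 weeks.

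**The concern.** A safety denominator normally includes everyone exposed to the device. Here the only set on offer removes some exposed subjects because of what happened after exposure. Protocol 8.5 lists an AE that makes continuation impossible or inadvisable among the reasons for withdrawal, so the exclusion can be triggered by the event that the table is meant to count. Removing a subject with an event lowers the rate.

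The exclusion also gains nothing in these tables, because a life table handles short follow-up by censoring. Withdrawn subjects are not replaced (Protocol 8.5), so in a single arm of about 30 one lost event is visible in the result. Safety, as reported through AEs and secondary surgeries, is a stated secondary objective in both documents.

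**Working it through.** **1. Which set can the AE tables use?** The per-protocol set is confined to overall success, which leaves the primary set. Two readings of its exclusion are possible.

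- *Narrow:* it applies only to the serum-metal analyses, which SAP 7.8.1 introduces with "The primary measurement analyses associated with the primary objective include". The AE and secondary-surgery life tables then have no stated population.
- *Wide:* it applies to clinical outcomes as well. The structure of the SAP supports this, because a subset of the primary set is used for overall success, a secondary outcome that itself includes serious implant-related AEs. Implanted subjects without follow-up then drop out of the AE rates, contrary to Protocol 9.15.3.

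Either way text is missing.

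**2. Can an affected subject have an AE on record?** Yes. AEs are documented at surgery/discharge, and the earliest in-window follow-up visit is at 6 − 2 = 4 weeks. Secondary surgery is less exposed: its form starts at the 6-week visit (Table 2), and Protocol 11.1.3 has index-level cases followed.

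**3. Size.** The plan has no AE rate, early-exit rate or precision target to reproduce. Its only figure is 30 enrolled (Protocol 8.1), with no formula behind it. All event and exit counts below are assumed. So is 25 implanted, a case included because enrolment is counted at consent (Protocol 8.2) and withdrawals are not replaced.

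Let N be the number implanted. One subject has an event and exits early, and m others have an event. The all-implanted rate is (m+1)/N; the primary-set rate is m/(N−1). Intervals are exact (Clopper-Pearson) 95%.

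| N | m | All implanted | Primary set | Drop (points) |
|---|---|---|---|---|
| 30 | 0 | 1/30 = 3.3% (0.1–17.2) | 0/29 = 0% (0–11.9) | 3.3 |
| 30 | 2 | 3/30 = 10.0% (2.1–26.5) | 2/29 = 6.9% (0.8–22.8) | 3.1 |
| 30 | 5 | 6/30 = 20.0% (7.7–38.6) | 5/29 = 17.2% (5.8–35.8) | 2.8 |
| 30 | 14 | 15/30 = 50.0% (31.3–68.7) | 14/29 = 48.3% (29.4–67.5) | 1.7 |
| 25 | 0 | 1/25 = 4.0% (0.1–20.4) | 0/24 = 0% (0–14.2) | 4.0 |
| 25 | 2 | 3/25 = 12.0% (2.5–31.2) | 2/24 = 8.3% (1.0–27.0) | 3.7 |

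With no early exit the two sets coincide; for example, 0/30 (0–11.6) in both.

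**4. Does the life-table method alter this?** Actuarial estimates, N = 30:

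- Early exit with an event, then 2 later events: 1 − (29/30)(27/29) = 10.0% in all implanted, against 2/29 = 6.9% in the primary set.
- Early exit without an event, then 2 later events: 2/29 = 6.9% in both.
- Early exit without an event, 2 events in the same interval: 2/(30 − 0.5) = 6.8% against 2/29 = 6.9%.

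So the choice of set matters only when the excluded subject had an event, and then it moves the rate down.

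**5. How likely is an early exit?** Under assumed per-subject rates, the chance of at least one among 30 is 1 − (1 − p)^30: 26% at p = 1%, 60% at 3%, 79% at 5%. These are chances of any early exit; that the subject also had an AE is a further condition.

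**The case against.** The link between the exclusion and the AE tables is made by elimination. The SAP never says these tables use the primary set. Its reference to all AEs, read with Protocol 9.15.3, could be taken to mean every implanted subject. That stands as a reason to call the loss possible and not certain. It does not supply a denominator.

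The affected group is narrow and may be empty. Under Protocol 9.6 a subject counts as discontinued only after notifying the site and with no later data; simple non-return does not qualify. Sites make at least three contact attempts after a missed visit (8.5), and AEs found outside scheduled visits are reported (9.5). What counts as postoperative follow-up is undefined, so a subject with a later reported event might be kept. This too stands.

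The effect is small beside the uncertainty. At N = 30 the drop is 1.7 to 3.3 points, against intervals in those rows about 12 points wide (0–11.9) to 38 points wide (29.4–67.5), with no hypothesis, comparator or AE threshold. Events also stay visible elsewhere: all AEs are reportable, aggregate safety data are reviewed at least annually (both Protocol 11.2), AE data go to FDA annually (9.15.3), and deaths and withdrawals appear in the accountability table (SAP 7.1.1). All true, but none of these routes puts a lost event back into the life-table rate.

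Finally, an all-implanted set still leaves out AEs from abandoned implantations. Protocol 9.6 already sends those to a summary of discontinuations and does not count the subjects, so that is a choice the protocol has made.

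**Conclusion.** The concern holds. The SAP has no safety set, the AE and secondary-surgery life tables name no population, and the one set that could serve them carries an exclusion that can depend on the AE itself. On one reading this conflicts with Protocol 9.15.3; on the other the tables have no denominator.

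On assumed counts, one early exit with an event lowers the rate by 1.7 to 3.3 points with 30 implanted, or 3.7 to 4.0 points in the two cases with 25, and can turn a single observed event into none. The effect is zero if nobody exits early, and negligible if the subject who exits had no event. The gap is confined to secondary, descriptive rates. It should be fixed because the exclusion has no analytic benefit in these tables.

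**What to change.** - In SAP 7.1.3, add a safety set: all subjects implanted with the device, whatever their later follow-up.
- Name it in 7.2.2, 7.8.2.7 and 7.8.2.8 as the population for every AE and secondary-surgery life table, with time counted from surgery and censoring at last contact.
- State in 7.1.3.1 that the exclusion for lack of follow-up applies only to metal concentrations and scores.
- Keep abandoned implantations in the summary of discontinuations, as Protocol 9.6 provides, and out of this denominator.

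The cost is SAP wording. The forms are already collected, and the set agrees with Protocol 9.6, so no protocol amendment is needed. Reported rates may look slightly less favourable, and the safety tables may have a different denominator from the outcome tables, which needs a footnote.

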### **9.16 Clinical Laboratory Tests**

All subjects enrolled in this clinical study, who undergo surgical treatment with the Prestige LP™ Cervical Discs will be required to have their blood drawn at specified time intervals, to be analyzed for metal concentrations. Each blood serum sample will be analyzed for the concentration of titanium, vanadium and aluminum. The metal concentrations at each postoperative evaluation will be summarized using descriptive statistics and will be compared against the preoperative baseline measurements. Guidelines specific to the blood collection procedure and metal concentration testing procedure are provided as an attachment to this protocol in Appendix I.

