## 11.1.3 Secondary Surgical Interventions

Some AEs or treatment failures may lead to a secondary surgical intervention at an operated index level. Information on the types of secondary surgical interventions is provided in the section below. Secondary Surgical Interventions will be classified by Medtronic. All patients undergoing a secondary surgical intervention at any operated index level will be followed.

- **Revision:** A procedure that adjusts or in any way modifies either one or both of the original implant configurations (e.g., adjusting position of the original configuration, removal with replacement with the same type of study implant). A revision will be classified as a treatment "failure".**Removal:** A procedure that removes one or more components of the original implant configuration without replacement with the same type of trial implant. Removals will be classified as either elective or non-elective. An elective removal is a procedure that removes the Prestige LP™ Cervical Disc(s) at the discretion of the investigator and/or the patient. An elective removal will not be classified as a treatment "failure." An elective removal is not considered an SAE. A non-elective removal is any removal other than an elective removal and is considered an SAE and will be classified as a treatment "failure."

NOTE: In the event that an implant requires a removal (explant), specific information and instructions are to be followed for this process. The instructions and information regarding the process is provided in the "Procedure for Retrieval, Handling and Packaging" included as an attachment to this protocol in **Appendix II**. All explanted devices will be analyzed along with histological evaluation of any retrieved peri-prosthetic tissue under the Post-approval Device Failure study (Explant Analysis) for the two-level indication.

- **Supplemental Fixation:** A procedure at the involved level(s) in which additional spinal devices not approved as part of the protocol are placed. A supplemental fixation will be classified as a treatment "failure."
- **Reoperation:** Any surgical procedure at the involved level(s) that does not remove, modify, or add any components and is not considered a removal, revision, or supplemental fixation. A reoperation, elective removal or other surgical procedure will not be classified as a treatment "failure."
- **Other:** Any surgical procedure not classified as a revision, removal, supplemental fixation or reoperation.

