## **13 Statistical Design and Methods**

Since there is not statistical hypothesis, the analyses will be descriptive in nature. In general, the categorial variables will be summarized using frequency tables and continuous variables will be summarized using mean, standard deviation, median, minimum, and maximum.

All data analyses will be based on observed data; missing data will not be imputed.

Changes in metal concentration and other scores from preoperative will be assessed by using paired t-test for normally distributed data or Wilcoxon signed rank test for not normally distributed data.

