### 13.2 Handling of Missing Data

All data analysis will be based on observed data; missing data will not be imputed.

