7.2 General Methodology

7.2.1 Laboratory Data and Analysis

Data of the metal concentrations in serum generated by the labs will be documented and provided to Medtronic, and the summary statistics (n, mean, median, standard deviation, minimum and maximum) at each time point will be presented. The changes in metal concentrations from preoperative at each post-operative visit will be analyzed using paired t-test for normally distributed data or Wilcoxon signed rank test for not normally distributed data. Further analysis on simple correlation of the metal concentration with continuous clinical outcome scores (NDI, neck pain, arm pain, and SF-36 PCS) and subgroup analysis on the metal concentrations by binary outcomes (neurological success, NDI success and overall success) will be carried out.

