7.4 Handling of Missing Data and Dropouts

Missing data due to missed follow-ups, lost to follow-ups (dropouts), or failure to answer CRF questions during office visits will not be imputed for analyses. Therefore, only observed data are analyzed.

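### SAP 7.1.3.1 carries pre-failure data forward after a secondary surgery failure without naming endpoints, so as written it reaches the primary serum-metal analysis and conflicts with the observed-data-only rule

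*SAP*

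**What the plan says.** SAP 7.1.3.1 defines the primary analysis dataset. It first says that missing data are not imputed and that observed data are used, then adds: "However, the data prior to the secondary failure will be carried forward to the latest visit for those who had a secondary surgery failure". No endpoint is named.

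The protocol has no such exception. Section 13 states: "All data analyses will be based on observed data; missing data will not be imputed". Section 13.2 repeats it: "All data analysis will be based on observed data; missing data will not be imputed". SAP 7.4 lists missed visits, dropouts and unanswered form items as not imputed and ends: "Therefore, only observed data are analyzed".

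For the metals, SAP 7.2.1 says "the summary statistics (n, mean, median, standard deviation, minimum and maximum) at each time point will be presented", and SAP 7.8.1 adds change from preoperative, a two-sided paired test, and a comparison by outcome: "Subgroup analysis of the metal concentrations by binary outcomes including overall success, NDI success and neurological success will be carried out". Neither section mentions secondary surgery. Serum is drawn preoperatively, at 6 weeks and at 12 months (Protocol 9.1, Table 2).

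On what happens after a secondary surgery, Protocol 11.1.3 says: "All patients undergoing a secondary surgical intervention at any operated index level will be followed". Protocol 9.16 says that subjects treated with the discs "will be required to have their blood drawn at specified time intervals, to be analyzed for metal concentrations".

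**The concern.** The only analyses that the SAP labels primary are those of serum titanium, vanadium and aluminum, so a rule written into the primary analysis dataset applies to them unless something says otherwise. Nothing does. SAP 7.1.3.2 shows that scope was stated where a limit was intended: it confines the per-protocol analysis to overall success.

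For metals, carrying forward means putting a 6-week concentration, or possibly a pre-implant one, in the 12-month cell. The subjects affected are those whose device was revised, non-electively removed or supplemented. Their serum is of particular interest in a study that FDA required in order to measure metal (Protocol 6.3) and whose stated benefit is to assess safety concerns from metal in the blood (Protocol 10.2).

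The rule also depends on a label. Under Protocol 11.1.3 a non-elective removal is a failure and would be carried forward. An elective removal is not a failure and would be analysed as measured.

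Two statisticians working from this text could build different 12-month tables from the same data.

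**Working it through.** **Reading the text.** Two readings are possible.

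- *Replace:* every visit after the failure takes the last pre-failure value, even if serum was drawn.
- *Fill only:* the carried value is used only where the visit is absent. The sentence is framed as an exception to a rule about missing data, which gives this reading some support.

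Both put unobserved values in the table, so both depart from Protocol 13 and 13.2 and from the last sentence of SAP 7.4. The SAP does not choose between them.

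**Inputs.** N = 30 is from SAP 6. The documents give no failure rate and no expected concentrations, so there is no plan figure to reproduce and the rest is assumed. Titanium is taken as 0.3 ng/mL preoperatively, 1.0 at 6 weeks and 1.5 at 12 months, with every non-failing subject identical. The ordinary 12-month change is 1.5 − 0.3 = 1.20. A carried 6-week value gives 1.0 − 0.3 = 0.70. A carried preoperative value gives 0; this arises only for a failure before the 6-week draw, and only if baseline counts as carriable data.

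**Formula.** With k failures, a true failure value x, and a carried change c of 0.70 or 0:

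- observed mean = [(30 − k) × 1.20 + k × (x − 0.3)] / 30
- carried mean = [(30 − k) × 1.20 + k × c] / 30

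For k = 1 the carried means are (34.8 + 0.70)/30 = 1.18 and 34.8/30 = 1.16. For k = 2 they are (33.6 + 1.40)/30 = 1.17 and 33.6/30 = 1.12.

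| True 12-month value in failures | k | Observed mean change | 6-week carried | Preoperative carried |
|---|---|---|---|---|
| 1.5 (ordinary) | 1 | 1.20 | 1.18 (−1.4%) | 1.16 (−3.3%) |
| 1.5 | 2 | 1.20 | 1.17 (−2.8%) | 1.12 (−6.7%) |
| 10 (high) | 1 | 44.5/30 = 1.48 | 1.18 (−20%) | 1.16 (−22%) |
| 10 | 2 | 53.0/30 = 1.77 | 1.17 (−34%) | 1.12 (−37%) |
| 0.3 (back to baseline after removal) | 1 | 1.16 | 1.18 (+2.0%) | 1.16 (none) |
| 0.3 | 2 | 1.12 | 1.17 (+4.2%) | 1.12 (none) |

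In the high case the reported maximum concentration also drops from 10 to 1.5.

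**Fill-only reading, 12-month draw missing.** One failure changes n = 29 with mean 1.20 to n = 30 with mean 1.18 or 1.16. Two failures change n = 28 with mean 1.20 to n = 30 with mean 1.17 or 1.12.

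**Metals by overall success.** A secondary surgery failure is by definition an overall failure (SAP 7.8.2.1), so every carried value falls in the failure group. Assume 6 overall failures, one of them a secondary surgery failure with true value x. The observed group mean is (5 × 1.5 + x)/6. The carried means are (7.5 + 1.0)/6 = 1.42 and (7.5 + 0.3)/6 = 1.30.

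- x = 1.5: 1.50 becomes 1.42 or 1.30 (−6% or −13%).
- x = 10: 2.92 becomes 1.42 or 1.30. The group moves from above to below the success group's 1.50.
- x = 0.3: 1.30 becomes 1.42 with the 6-week value carried (+9%).

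**Chance that the rule is used at all.** P(at least one failure in 30) = 1 − (1 − p)^30. For assumed 12-month failure rates of 1%, 2%, 5% and 10% this is 26%, 45%, 79% and 96%.

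**The case against.** Within SAP 7.1.3.1 the rule is a declared exception, and the reasons listed in SAP 7.4 do not include secondary surgery, so that list can stand beside it. The authors may have had clinical outcomes in mind. This narrows the firm conflict to Protocol 13 and 13.2 and the closing sentence of 7.4. It does not remove it, because an exception declared in one SAP paragraph does not amend the protocol.

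That a measured 12-month value will exist is an inference. Protocol 11.1.3 promises follow-up without mentioning serum, and Protocol 8.5 and 9.6 stop data collection for withdrawn or discontinued subjects. The inference is reasonable given Protocol 9.16, but the largest effects depend on it, since they require a measured value to be overwritten.

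The size objection largely stands. At ordinary levels the mean moves by at most 6.7% with two failures. The large effects and the reversed group order need an assumed 10 ng/mL and, for the reversal, one secondary surgery failure among six overall failures. The median change stays at 1.20, but that is built into a model with identical non-failing subjects, which also says nothing about the SD or the paired tests. The study is descriptive, and the by-success comparison carries no inference.

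SAP 8 has two independent statisticians compare outputs and resolve discrepancies. That would catch a disagreement, but it gives no rule to settle it, and the choice would then be made with the data in view.

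**Conclusion.** The concern holds and should be fixed. Followed exactly, the sentence puts an earlier concentration in the 12-month cell of the primary measurement for every secondary surgery failure, against a protocol rule that admits no exception. Whether it was meant to cover metals is unclear, and that is itself part of the defect.

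The numerical effect is nil with no failures, a few percent of the mean change with one or two ordinary failures, and 20% to 37% only if failing subjects have very high serum titanium. The error is downward if the true later value exceeds the carried one and upward if it is lower, as may happen after a removal. It is concentrated in the failure group of the metals-by-overall-success comparison. All these sizes rest on assumed titanium levels and failure counts. The textual conflict does not.

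**What to change.** In SAP 7.1.3.1, replace the open-ended sentence with one that names the clinical outcomes to which carry-forward applies, for example overall success counted as failure from the date of the secondary surgery failure. State that it does not apply to serum titanium, vanadium or aluminum, which are analysed as observed. Flag or list every metal value drawn after any secondary surgery or removal, elective removals included, so that readers can see these subjects separately. Align 7.1.3.1 with SAP 7.4 and Protocol 13 and 13.2, so that any remaining exception for clinical outcomes appears in each place.

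The cost is one SAP sentence, matching cross-references and a short listing. No new visits, samples or subjects are needed. The 12-month metal figures could move in either direction as a result. If failing subjects have high concentrations, the figures will look less favourable.
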